## 5 STUDY DESIGN

### 5.1 Overall Design

This is a Phase 3, multicenter, randomized, double-blind, placebo-controlled study to assess the safety and efficacy of posoleucel as compared to placebo for the treatment of AdV infection in pediatric and adult recipients of HCT with AdV infections receiving SoC.

Approximately 82 participants at approximately 50 clinical sites in the US, Europe, and Canada who meet all of the inclusion criteria and none of the exclusion criteria may be enrolled into the study and randomized █ to receive posoleucel or placebo. Randomization will be stratified █

█ It is expected that no more than 30% of participants, but at least 10% of participants, will be  $\geq 18$  years of age.

Enrollment of participants  $<1$  year of age will occur once preliminary safety data are available from 5 participants  $\geq 1$  and  $\leq 6$  years of age. On 16May2023, the DSMB reviewed data from 6 participants aged 1-6 years that have completed through D29 and recommended opening enrollment to patients  $<1$  year of age. An additional meeting will be held once 6 patients  $<1$  year old have been enrolled and completed through D29 of the study.

Posoleucel is to be administered at a fixed cell dose based on weight, as █ sequential infusions separated by █ (see [Section 7.1](#)).

The Primary Study Period is 4 weeks (28 days) for evaluation of efficacy, including the primary endpoint, plus 20 weeks for safety follow-up, for a total study duration of 24 weeks. For participants who cross over, the Cross-Over Period is 4 weeks (28 days), plus 20 weeks for safety follow-up. Participants who experience recurrence and receive an additional dose will have safety follow-up for 20 weeks after the additional dose of study treatment.

At Day 29, all participants will be assessed for the primary endpoint, virologic response.

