#### Option for Cross-Over

Participants who progress to active target organ disease or whose existing target organ disease progresses (assessed by the Investigator and Sponsor Medical Monitor and based on the criteria in [Appendix 8](#)) between Day 29 and Week 10 will be considered to have experienced progression and will have the option to be crossed over to the alternate treatment arm.

Participants can cross over before Day 29 only if they progress as adjudicated by the Adjudication Committee. For potential cases of premature cross-over (ie, prior to Day 29), participants will be expected to have received both infusions of study treatment before evaluation by the Adjudication Committee. Cross-over participants will receive the alternate treatment to which they were originally randomized, posoleucel or placebo (█ sequential infusions separated by █ but study treatment will remain blinded. Participants must meet the following eligibility criteria to cross-over: participant must not have evidence of acute GVHD Grade 3 or higher (Exclusion Criterion 1), must not be receiving ongoing therapy with high-dose systemic corticosteroids  $>0.5$  mg/kg/day prednisone or equivalent unless approved by Medical Monitor (Exclusion Criterion 2) and must not have experienced a severe infusion-related reaction (Grade  $\geq 3$ ) with the prior doses of study treatment (posoleucel or placebo).

If the participant receives any antiviral drugs in violation of the protocol during the study, that participant will be included in the primary analysis, but will not be eligible for cross-over. Follow-up will be continued for safety and persistence of the virus-specific T cells (VSTs).

Participants must meet all of the cross-over eligibility criteria by Week 10 of the Primary Study Period to enter the Cross-Over Period. A new baseline (Day 1' of the Cross-Over Period) will be established at the time of the first cross-over infusion. At Day 29' of the Cross-Over Period, participants will be assessed for clinical and virologic response. The participants will then have 20 weeks of safety follow-up, for a total duration of 24 weeks for the Cross-Over Period. The maximum study duration for participants who cross over is 34 weeks, including up to 10 weeks in the Primary Study Period and 24 weeks in the Cross-Over Period.

Participants who cross over are not eligible to receive treatment for recurrence (described below).

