#### Recurrence

Participants who demonstrate viral clearance by Day 29 of the Primary Study Period but later exhibit a clinically significant recurrence of AdV viremia (ie,  $\geq 10,000$  copies/mL AdV DNA at the central laboratory) and/or progression of or to active organ disease, will be eligible for an additional dose of the last received therapy (posoleucel or placebo) for recurrence prior to 20 weeks. These participants will continue to have safety follow-up for an additional 20 weeks after administration of the additional dose. The visit in which the participant receives the additional dose for recurrence should mimic the assessments performed on [REDACTED] Participants who receive an additional dose for recurrence will be monitored using the schedule as specified in the Primary Study Period schedule of events starting at the Week 5 visit, which should occur 1 week after infusion of the additional dose. This applies even if the participant completed any of these visits prior to receiving the additional dose.

A summary of the study design is shown in [Figure 1](#).

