3 STATISTICAL METHODOLOGY

3.1 General Considerations

The statistical analysis of the data obtained from this study will be performed using SAS® version 9.4 or higher.

Data collected in this study will be documented using summary tables and subject data listings. Continuous variables will be summarized using descriptive statistics, specifically the number of non-missing observations, mean, standard deviation, median, minimum, and maximum. Categorical variables will be summarized using the frequency count and the percentage of participants in each category. For continuous data, the minimum and the maximum will use the same decimal place accuracy as the raw data. The mean, median, and standard deviation will use one more decimal place than the raw data. For categorical data, percentages will be reported to one decimal place.

Summary statistics will be presented by randomized or actual treatment group for the Primary Study Period. The key efficacy and selected safety endpoints will be summarized for the Primary Study Period.

No hypothesis tests will be performed.

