3.5 Safety Analyses

Safety will be analyzed and compared between treatments received based on data from the Primary Study Period. No formal comparisons will be made between these groups.

All safety analyses will be based on the Safety Population.

Categorical endpoints will be summarized using the number and percentage of participants within each category. Continuous endpoints will be summarized descriptively with summary statistics (number of non-missing observations, arithmetic mean, standard deviation, median, minimum, and maximum).

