3.5.1 Adverse Events (AEs)

All AEs will be coded to system organ class and preferred term using MedDRA. A treatment-emergent adverse event (TEAE) is defined as an adverse event with a start date and time on or after the administration of investigational product or placebo or that worsened in severity after administration of investigational product or placebo through the end of the study.

An overall summary of AEs will be provided with the number and percentage of participants who experienced at least one (1) AE or TEAE in the following categories:

- Any TEAEs
- Any TEAEs by severity
- Any treatment-related TEAEs
- Any treatment-related TEAEs by severity
- Any treatment-emergent AESI (TEAESIs)
- Any treatment-emergent serious AEs (TESAEs)
- Any treatment-related TESAEs
- Any TEAEs leading to discontinuation of study treatment
- Any TEAEs leading to discontinuation of study, and
- Any AEs leading to death

The numbers and percentages of participants will also be presented by system organ class (SOC) and preferred term (PT) for each of the TEAE categories in the summary. Participants with multiple AEs will be counted only once per SOC and PT.

Listings will be presented specifically for any AEs, SAEs, AESIs, and AEs leading to discontinuation of study treatment and study.

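### Adverse events are shown only as crude percentages over the Primary Study Period, whose length depends on outcomes that may differ by arm

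*SAP*

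**What the plan says.** Incidence and severity of treatment-emergent adverse events (TEAEs) is the primary safety endpoint (Protocol 4 and 10.3.2; SAP 2.3.2). On the comparison, SAP 3.5 states: "Safety will be analyzed and compared between treatments received based on data from the Primary Study Period". It then adds: "No formal comparisons will be made between these groups". SAP 3.1 says: "No hypothesis tests will be performed".

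The measure in SAP 3.5.1 is the number and percentage of participants with an event: "The numbers and percentages of participants will also be presented by system organ class (SOC) and preferred term (PT"). SAP 3.5.2 does the same for graft versus host disease (GVHD), cytokine release syndrome, infusion-related events and graft failure. Protocol 10.3.2 matches. Neither document mentions time at risk, exposure-adjusted rates, time to first event or a fixed cut-off day. The TEAE definition covers events that start on or after dosing or that "worsened in severity after administration of investigational product or placebo through the end of the study".

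Three lengths of observation follow from Protocol 5.1:
- Standard: 4 weeks "plus 20 weeks for safety follow-up, for a total study duration of 24 weeks".
- Cross-over after progression: "The maximum study duration for participants who cross over is 34 weeks, including up to 10 weeks in the Primary Study Period".
- Third dose after clearance and recurrence: "These participants will continue to have safety follow-up for an additional 20 weeks after administration of the additional dose".

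**The concern.** A crude percentage mixes the event rate with the length of observation. Cross-over follows progression, which is the key secondary endpoint. The third dose requires clearance, which is the primary endpoint, followed by recurrence. Follow-up in the Primary Study Period therefore depends on the outcomes that the product was meant to change. If one arm progresses and crosses over more often, its participants are watched for less time and show fewer events at the same underlying risk. The arm with the better efficacy then looks less safe. Cutting correctly at Day 1' (the first cross-over infusion) does not help, because that cut is what shortens the follow-up.

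The rows at stake are mainly those for late events, such as chronic GVHD, and any table of TEAEs or serious events accumulated to Week 24. Under the SAP these tables are the only side-by-side safety display in the abbreviated report.

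**Working it through.** The documents state no TEAE rate, cross-over share or person-time, so there is no plan figure to reproduce. What follows shows the mechanism under stated assumptions.

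**Inputs from the documents.** Primary Study Period 24 weeks; at most 10 weeks for those who cross over; 20 weeks of follow-up after a third dose (Protocol 5.1). Clearance 0.55 on posoleucel and 0.25 on placebo (Protocol 10.1). 41 per arm planned (Protocol 5.2).

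**Assumptions.** The same constant hazard λ in both arms. Cross-over at Week 6. Third dose in 10% of clearers at Week 12, hence 5.5% and 2.5% of participants, followed to Week 12 + 20 = 32, with those events counted.

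**Formula.** Crude percentage = Σ share × (1 − exp(−λT)), with T = 6, 24 or 32 weeks.

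**Base case**, λ = 0.03 per week, cross-over 25% on placebo and 10% on posoleucel:
- 1 − exp(−0.03T) = 0.1647 at 6 weeks, 0.5132 at 24 and 0.6171 at 32.
- Placebo: 0.25 × 0.1647 + 0.725 × 0.5132 + 0.025 × 0.6171 = 42.9%.
- Posoleucel: 0.10 × 0.1647 + 0.845 × 0.5132 + 0.055 × 0.6171 = 48.4%.
- Spurious excess: 5.5 points, or 0.055 × 41 ≈ 2.3 participants.
- Mean planned observation: 0.25 × 6 + 0.725 × 24 + 0.025 × 32 = 19.7 weeks on placebo; 0.10 × 6 + 0.845 × 24 + 0.055 × 32 = 22.6 weeks on posoleucel.

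**Grid**, spurious excess on posoleucel in points (posoleucel cross-over 10%, third-dose shares as above):

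| λ per week | placebo cross-over 20% | 25% | 35% |
|---|---|---|---|
| 0.01 | 1.7 | 2.5 | 4.1 |
| 0.03 | 3.8 | 5.5 | 9.0 |
| 0.05 | 4.7 | 6.9 | 11.3 |

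**Checks.**
- Equal use (cross-over 20% and third dose 5% in both arms): difference 0.0.
- Third dose removed from the base case: 47.8% against 42.6%, or 5.2 points. That leg adds about 0.3. SAP 2.2.4 prints a posoleucel clearance rate of 0.50; a 5.0% share instead of 5.5% changes the result by 0.005 × (0.6171 − 0.5132) ≈ 0.05 points.
- Cross-over shares reversed, no third dose: −5.2 points. The sign follows the imbalance.
- Different assumptions (24-week incidence 30%; cross-over at Day 50 in 10% of posoleucel and 30% of placebo; third dose in 5.5% and 2.5%, to Day 224): 28.4% against 24.2%, or 4.2 points. With 50% or 80% of the risk placed in the first 28 days, this falls to 2.4 or 0.9 points.
- Person-time, base case: expected time to first event or end of observation is Σ share × (1 − exp(−λT))/λ = 14.29 weeks on placebo and 16.14 on posoleucel. Rates are 0.4287/14.29 and 0.4841/16.14, both 3.0 per 100 participant-weeks. The artefact disappears when the hazard is constant and leaving is unrelated to event risk.

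**The case against.** **The imbalance is hypothetical.** A reader might infer that observation time depends on treatment arm, or that the posoleucel safety tables are biased. The documents support neither. Time depends on outcome, and no cross-over or third-dose rate by arm is given. SAP 1 says the trial stopped for futility, so the efficacy difference behind the illustrative shares cannot be presumed. This stands. Equal cross-over cannot be presumed either, and an imbalance in either direction distorts the percentages.

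**Not every progressor leaves.** Cross-over is optional. It is barred for Grade 3 or higher acute GVHD, a Grade 3 or higher infusion reaction or a protocol-violating antiviral, and for high-dose steroids unless the Medical Monitor approves (Protocol 5.1). Progressors who decline or are ineligible stay in the period. This stands. It lowers the plausible cross-over shares but does not remove the mechanism.

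**The third dose.** A reader might also give the extension equal weight with cross-over. It adds about 0.3 points, and it is unclear whether its events count. Protocol 9.2.1 collects events until the Week 24 visit, or Week 24' after cross-over. Protocol 5.1 restarts third-dose participants at the Week 5 visit, so that visit could be read as the scheduled one or the repeated one.

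**The tables are descriptive.** There are no tests, and SAP 3.3.1 already reports numbers entering cross-over and recurring, so a reader could notice an imbalance. That limits the seriousness. But side-by-side percentages are still read as a comparison, and counts of cross-over do not give time at risk.

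**Rates have their own flaw.** Cross-over follows progression, so ending time at risk at Day 1' is informative censoring, and a single rate suits infusion reactions poorly. This stands and shapes the fix.

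**Conclusion.** The point holds in a limited form. TEAEs and events of special interest are shown only as crude percentages over a period that cross-over shortens from 24 weeks to at most 10, so equal hazards give unequal percentages whenever cross-over differs by arm. Under the assumed constant hazards and cross-over shares the artefact is about 1.7 to 11.3 points, 5.5 in the base case. It is zero when cross-over and third-dose use are equal, and about 1 point when most of the risk falls in the first four weeks. All hazards, shares and exit times are assumptions. The documents do not show that an imbalance occurred or which way it would run. For a descriptive report of a trial stopped for futility, this is a worthwhile low-cost improvement. It does not invalidate the planned tables.

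**What to change.** In SAP 3.5.1 and 3.5.2, keep the crude tables and add:

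1. As the main side-by-side display, TEAEs and events of special interest with onset from Day 1 to Day 29, or to the day before Day 1' if earlier. Observation is nearly common there, because earlier cross-over requires adjudicated progression.
2. Person-time by arm, and participants with a first event per 100 participant-weeks. Time at risk ends at the first of event, Day 1', last contact or Week 24. Show events after a third infusion separately; do not drop them.
3. A statement that cross-over after progression is informative censoring, so the rates are supportive only.
4. A rule that reconciles the TEAE window, which runs to the end of the study (SAP 3.5.1), with the Primary Study Period basis of the comparison (SAP 3.5), and that says whether events in the third-dose extension are collected and counted (Protocol 9.2.1 against the Recurrence text in Protocol 5.1 and SAP 2.2.1).

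Cost: SAP wording, one derived time-at-risk variable and a few extra tables; no new data. Limits: the Day 29 window misses late events such as chronic GVHD, for which the crude table and the rates are still needed, and the rates assume a roughly constant hazard.

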3.5.2 AEs of Special Interest

The AESIs will be reviewed by the DSMB as per the DSMB Charter. Criteria for acute and chronic GVHD and CRS can be found in Protocol Appendix 6 and 7, respectively.

The number and percentage of participants who had the treatment-emergent AESIs will be summarized by treatment group for the Primary Study Period and by cross-over treatment group for the Cross-Over Period:

- Severity and incidence of acute GVHD
- Severity and incidence of chronic GVHD
- Severity and incidence of CRS (ASTCT Score)
- Severity and incidence of infusion-related AEs
- Severity and incidence of graft failure and rejection

3.5.3 Clinical Laboratory Tests

Clinical laboratory data (hematology, clinical chemistry, and routine urinalysis) from the Primary Study Period will be summarized by laboratory test, visit, and treatment group using descriptive statistics. The changes from baseline to each post-baseline visit will also be summarized.

Listings will be presented for selected laboratory data and the test values outside the normal range will be flagged.

3.6 Data Safety Monitoring Board

An independent Data and Safety Monitoring Board (DSMB) will be convened for this study to routinely monitor participant safety. The DSMB will receive summary reports of all unexpected SAEs at least monthly. A DSMB charter, detailing all aspects of the DSMB's composition, scope of review, and procedures will be provided separately. An unblinded statistician will be assigned to the DSMB. This statistician will not be involved in any aspects of study conduct outside of the DSMB, and their role will be defined in the DSMB charter.

3.7 Interim Analysis

A Sample Size Re-Estimation (SSRE) and futility analysis will be performed after approximately 40 participants have completed Day 29 of the Primary Study Period. Details of the SSRE and futility analysis will be provided in the SSRE Plan prior to conducting the interim analyses.

Appendix 1 Analysis Visit Windows

Table 1 Analysis Visit Windows for Adenovirus Viral Load Data

Nominal Visit	Nominal Study Day	Visit Window Study Day	
		Lower Limit	Upper Limit
Day 1/Baseline	1		≤1
Week 1	8	2	11
Week 2	15	12	18
Week 3	22	19	25
Week 4	29	26	32
Week 5	36	33	39
Week 6	43	40	57
Week 10	71	58	92
Week 16	113	93	141
Week 24	169	>141	

Table 2. Analysis Visit Windows for Other Viral Load and Clinical Lab

Nominal Visit	Nominal Study Day	Visit Window Study Day	
		Lower Limit	Upper Limit
Day 1/Baseline	1		≤1
Week 1	8	2	11
Week 2	15	12	22
Week 4	29	23	36
Week 6	43	37	57
Week 10	71	58	92
Week 16	113	93	141
Week 24	169	>141	

Signature Page for P-105 303 Final SAP v1.0 for abbreviate CSR
VV-CLIN-000364 v1.0

Approval Task	[REDACTED] ics 12-Jan-2024 19:11:42 GMT+0000
---------------	---

Approval Task	[REDACTED] 12-Jan-2024 21:26:04 GMT+0000
---------------	---

Signature Page for P-105 303 Final SAP v1.0 for abbreviate CSR
VV-CLIN-000364 v1.0
